### **6.4 Placental pathology and Chorioamnionitis Analysis**

Placentas from subjects will be sent to the surgical pathology department at each site in accordance with standard clinical care following delivery (sent in-total in a specimen container with formalin for fixation). Routine placental pathology will be performed and pathologists will be unaware of study group at the time of placental evaluation. Routine pathology reporting includes gross and microscopic evaluation of the placenta including weight, umbilical cord including length, diameter, number of vessels, coiling, and insertion point, fetal membrane characteristics.

Histologic chorioamnionitis is diagnosed using standard hematoxylin and eosin (H & E) staining to identify inflammatory cells (neutrophils, lymphocytes, eosinophils, etc.) as infiltration of the chorionic plate by neutrophils is diagnostic of chorioamnionitis. Chorioamnionitis is staged as per the grading system described below.

Table 5: Histologic Chorioamnionitis Grading Scheme		
Stage 1 – Mild	Stage 2 - Moderate	Stage 3 - Severe
Acute subchorioamnionitis or acute chorioamnionitis	Acute chorioamnionitis	Necrotizing chorioamnionitis

Characterized by neutrophils in subchorionic fibrin or interface between decidua and chorion	Neutrophils in connective tissue plane between chorion and amnion	Necrosis, amnion sloughing, thickening of amnion basement membrane and neutrophilic karyorrhexis, Multifocal abscesses may be present as well as funisitis (identification of neutrophils in the umbilical cord connective tissue)
--	---	--

For microscopic evaluation of chorioamnionitis, we use the 2003 Pediatric Pathology Society consensus recommendations to diagnose and stage chorioamnionitis (Redline, Raymond W., et al. "Amniotic infection syndrome: nosology and reproducibility of placental reaction patterns." *Pediatric and Developmental Pathology* 6.5 (2003): 435-448.).

## 7 STATISTICAL CONSIDERATIONS

In collaboration with the CDC and Cincinnati sites, the research team at Duke will oversee the statistical analysis. This pilot study is not designed based on statistical considerations regarding power/sample size in relation to group comparisons. Therefore, descriptive statistics and confidence intervals for continuous variables will be presented (e.g., mean, standard deviation, median, interquartile range, and confidence boundaries). Categorical variables will be summarized with frequencies, percentages, and exact confidence boundaries.

For analysis, data will reside on a secure Duke server maintained by Duke Health Technology Solutions (DHTS). For the study, a database will be developed and a dataset for the study without personal identifiers will be made available to the CDC upon request.

### 7.1 Analysis Plan

**7.1.1 Study Populations** – There will be two study populations for this study. The Intent-to-Treat (ITT) and Safety populations. The ITT Population includes any participant that was enrolled and randomized into the study. The Safety Population is a subset of the ITT Population excluding those participants that never received the study intervention (either the influenza or Tdap vaccine). Statistical analyses will be performed for both study populations, or the ITT Population only if no participants are excluded for the Safety Population.

**7.1.2 Primary Objective 1** - To assess proportions of reactogenicity events in pregnant women receiving Tdap and IIV simultaneously vs. sequentially

Reactogenicity will be assessed for 7 days following each vaccination visit, as described in Section 5.3. The proportion of women and a 95% exact binomial confidence interval will be presented by treatment group, symptom, and grade level (mild/moderate/severe) for women with injection site reactogenicity within 7 days post-vaccination. This will be presented for each of the four reactogenicity outcomes, using the highest grade reported per woman. A 95% confidence interval of the difference in proportions between the treatment groups will also be presented. Systemic reactogenicity will be presented in a similar fashion. For adverse events, the proportion of women and a 95% exact binomial

confidence interval of adverse events, as well as the total number of adverse events, will be presented by treatment group, severity, and relatedness

**7.1.3 Primary Objective 2** - To assess maternal immune responses and cord blood antibody levels to pertussis antigens, tetanus and diphtheria toxoids, and influenza antigens in the women receiving Tdap and IIV simultaneously vs. sequentially

**7.1.3.1 Pertussis antigens** - Geometric mean titers (GMTs) will be calculated along with 95% confidence intervals for the two treatment groups for each pertussis antigen tested. A 95% confidence interval of the difference in GMTs between the treatment groups will also be presented.

**7.1.3.2 Tetanus and diphtheria antigens** - The proportion of subjects with seroprotection, defined as  $\geq 0.1$  IU/mL post-vaccination for both tetanus and diphtheria ELISAs, in the two treatment groups will be presented along with 95% exact binomial confidence intervals. Ninety-five percent confidence intervals of these differences in proportions between the treatment groups will also be presented. Given there is no acceptable definition of seroconversion with these assays, we will evaluate the data to derive a potential post hoc definition for seroconversion.

**7.1.3.3 Influenza antigens** - The proportion of subjects with seroprotection (pre- and post-immunization) and seroconversion (4-fold change in endpoint titer relative to pre-immunization baseline or a change from  $<1:10$  to  $\geq 1:40$ ) in the two treatment groups will be presented along with 95% exact binomial confidence intervals. A 95% confidence interval of the difference in proportions between the treatment groups will also be presented. The GMTs for each influenza antigen and 95% confidence boundaries will be presented for both treatment groups. A 95% confidence interval of the ratios in GMTs between the treatment groups will also be presented.

Outcomes listed in Primary Objective 2 may be analyzed using a regression model to adjust for covariates such as BMI or race. This will be performed as a secondary analysis if normality assumptions for model based analyses are met.

**7.1.4 Primary Objective 3** – To assess the feasibility of conducting a larger clinical trial in pregnant women receiving Tdap and IIV simultaneously vs. sequentially

Feasibility will be assessed based on the following benchmarks for recruitment and retention in **Table 6**, as well as adequate and timely collection of data and biospecimens.

Table 6: Proposed Feasibility Benchmarks	
Benchmark	Completion Target
Recruitment and randomization	30-50* subjects during 4 month enrollment period
Retention	98% completion of all in-person and delivery visits
Data collection	$\geq 95\%$ collection of reactogenicity data
Biospecimen collection – maternal	$\geq 95\%$ collection of pre/post-vaccination blood samples

Biospecimen collection – delivery	≥ 95% collection of maternal blood, umbilical cord blood, and placental pathology
-----------------------------------	---

\*enrollment target will depend upon whether additional enrollment occurs at the Cincinnati Site

**7.1.5 Secondary Objective 1** – To describe maternal and infant outcomes in pregnant women receiving Tdap and IIV simultaneously vs. sequentially

The proportion and 95% exact binomial confidence interval will be presented by treatment group for adverse birth outcomes such as preterm birth, low birthweight and SGA. A 95% confidence interval of the difference in proportions between the treatment groups will also be presented.

**7.1.6 Secondary Objective 2** – To evaluate clinical and histological chorioamnionitis in the women receiving Tdap and IIV simultaneously vs. sequentially

The proportion and 95% exact binomial confidence interval will be presented by treatment group for histological and clinical chorioamnionitis. A 95% confidence interval of the difference in proportions between the treatment groups will also be presented.

**7.1.7 Secondary Objective 3** – To build capacity to study immunogenicity of maternal vaccination in the CISA Project, in collaboration with the CDC lab as described in **Table 7**.

**7.1.8 Exploratory Objective 1** - To assess antibody levels to pertussis antigens at 2 months of life in infants born to women receiving Tdap and IIV simultaneously vs. sequentially

Geometric mean titers (GMTs) will be calculated along with 95% confidence intervals for the two treatment groups for each pertussis antigen tested. A 95% confidence interval of the ratio in GMTs between the treatment groups will also be presented as well as for the infant cord blood versus the 2-month blood draw.

Table 7: Feasibility Benchmarks for CDC lab	
Benchmark	Completion Target
Quality of blood specimens submitted to the CDC lab for serologic response to pertussis antigen	Receipt of ≥95% of blood samples in testable condition
Quantity of blood specimens submitted to the CDC lab for serologic response to pertussis antigen	Receipt of ≥95% of blood samples with sufficient volume for testing
Completion of testing	Completion of testing of ≥95% of testable blood samples.

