## 5 STUDY SCHEDULE, PROCEDURES, & EVALUATIONS

### 5.1 Schedule of events

Pregnant women meeting the proposed eligibility criteria (Section 4.1-4.2) will be recruited. Written informed consent (Appendix I) will be obtained from study participants prior to conducting any study procedures. **Table 2** describes the proposed schedule of study visits with further details below.

Procedure	Screening Visit* Day -28 to 1	Visit 1 Day 1	Visit 2 Day 4 $\pm$ 1	Visit 3 Day 9 + 3	Visit 4 Day 22 + 7	Visit 5 Day 25 – 32 $\pm$ 1	Visit 6 Day 30 – 37 + 3	Visit 7 Day 43 -50 + 7	Visit 8 Delivery	Visit 9 Infant Blood Draw	Unscheduled Visit
Type of contact	Chart Abstraction/ Clinic	Clinic	Phone/ Email/ Text	Phone/ Email/ Text	Clinic	Phone/ Email/ Text	Phone/ Email/ Text	Clinic/ Phone/Email/ Text	Hospital/ Chart Abstraction	Clinic	Clinic
Informed consent & Medical Release of Information	X									X e	
Review Eligibility Criteria	X	X									
Review eligibility criteria for Tdap vaccination					X a						
Data Collection b	X	X	X	X	X	X	X	X	X		X
Influenza and Td/TT/Tdap Vaccination History	X										
Vital signs (temperature, heart rate, respiratory rate and blood pressure) c		X			X a						X

Collection of Cord Blood & Placenta									X		
Randomization		X									
Vaccination		X			X a						
Dispense and review instructions for Memory aid supplies & (REDCap or paper)		X			X						
Complete Memory aid form (REDCap or paper)		X	X	X	X	X	X				
Reactogenicity (local & systemic)			X	X		X	X				
Concomitant medications	X	X	X	X	X	X	X	X	X		X
Obtain solicited & unsolicited adverse events		X	X	X	X	X	X				X
Obtain medically-attended events and serious adverse events		X	X	X	X	X	X	X	X		X
Infant Data Collection d										X	
Infant Blood Sample (DBS)										X	
* Screening visit may occur simultaneously with Visit 1											
a Procedures for subjects in sequential group only											
b Data collection includes demographic information, medical and obstetric history, current pregnancy status. Changes in baseline medical status such as worsening or new onset condition will be capture as adverse events											
c Vital signs measured prior to vaccinations during Visit 1 and Visit 4											
d Data collection includes pertussis-specific medical history											
e Informed consent to be completed prior to Visit 9 blood draw											

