**Visit 4, Study Day 22 (window Days 22 – 29) Clinic Visit**

- For study participants in the sequential study group, review exclusion criteria listed in section 4.2 for Tdap vaccination
- Obtain vital signs including oral temperature prior to vaccination for study participants in the sequential group.
- Study staff will review the memory aid data and record any AEs, SAEs, concomitant medications, and current medical/pregnancy status as described in Section 5.1
- Obtain 15mL blood sample for serologic analysis (Section 6). Study participants in sequential group to have blood sample obtained prior to vaccination.
- For subjects in the sequential study group, trained, licensed research staff will administer Tdap as described in Section 5.2.3. Ensure participants receive Tdap Vaccine Information Sheets (VIS) during visit.
- Confirm subjects still have previously dispensed thermometer and ruler; if not, provide new supplies. Review instructions for use of thermometer, ruler, and memory aid (Appendix A) completion. All subjects will complete the memory aid (Appendix D and E) again to allow for the collection of “mock” data in the simultaneous group for comparison with the sequential group. Simultaneous group will only provide information for systemic reactions and oral temperature.

- Confirm preferred method of contact for follow-up (telephone or email reminder)
- Confirm date of next scheduled prenatal appointment

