### **5.3 Reactogenicity Assessment**

Frequency and occurrence of local and systemic reactogenicity, solicited and unsolicited AEs, SAEs, concomitant medication use, and unscheduled medical care will be assessed immediately after vaccination (day 1) through post-vaccination Day 8 (day 1-8) using a standard memory aid (Appendix B-E). At the time of study enrollment, participants will be given an oral digital thermometer and instructed on completing the memory aid to document oral temperatures and post-injection symptoms, daily. A study staff member will review each portion of the memory aid with the subject in order to familiarize the subject with the form. The subject will be given the choice of either entering their data into REDCap daily or utilizing a traditional paper memory aid. Subjects will be instructed to notify study staff promptly using the 24-hour contact number provided in the memory aid in the event of any severe (Grade 3) local or systemic reactions.

Beginning on the evening of Study Visit 1 (Day 1) following vaccination, participants will record their oral temperature using the study-supplied thermometer, the occurrence of AEs, and concomitant medication use for the next 7 days (Day 1 – 8). Temperature will be recorded at roughly the same time each day. If a temperature  $\geq 100.0^{\circ}\text{F}$  ( $37.8^{\circ}\text{C}$ ) is recorded, a second measurement will be taken within 20 minutes. If more than one temperature is taken on the same day, the highest temperature should be recorded. Solicited adverse events (local and systemic), which will be classified as mild, moderate, or severe as described in **Tables 3 and 4**, will be reviewed and recorded during Visits 2-3 and 5-6.

Each day, women will record reactogenicity data either on paper or directly into the REDCap system through 7 days post-vaccination. All subjects will be provided with a paper memory aid (Appendix B-E) to record their reactogenicity data for ease of recall when entering into REDCap or recalling to research staff over the phone. We have selected a reactogenicity period of vaccination day and the next seven days based on pre-licensure studies of Tdap and IIV vaccines in adults and adolescents which suggest

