Participants using the paper diary will be contacted at Visits 2-3 and Visits 5-7 to review and document the information recorded in their diary. They will also be encouraged to report unsolicited adverse events in an open-ended question format, e.g. "How are you doing? Are you having any medical or clinical problems? If so, please tell me about them." Participants who report severe solicited adverse events or express any concern about symptoms/unsolicited events will be encouraged to follow up with their ObGyn or primary care provider. Study staff will assist with coordination of referral appointments as necessary. Medical records will be obtained and reviewed for any unscheduled medical appointment through post-vaccination Day 8. The same procedures for solicited adverse events will follow the second vaccination for the sequential group and be performed around the same time period for the simultaneous group in a "mock" fashion (Visits 4-6, with the exception of solicited injection site reaction). After Visit 4, solicited injection site reactions will not be recorded by participants in the simultaneous group. After the reactogenicity assessment period, only medically-attended adverse events will be collected.

Table 4: System Reactogenicity			
Systemic	Mild (Grade 1)	Moderate (Grade 2)	Severe (Grade 3)
Oral Temperature (°C/°F)**	≥ 37.8 - ≤ 38.7° C ≥ 100.0 - < 102.0 °F	≥ 38.8 - ≤ 39.4° C ≥ 102.0 - ≤ 103.0° F	≥ 39.5° C ≥ 103.1° F
Fatigue (Malaise)	Noticeable but does not interfere with activity	Interferes with activity but did not necessitate medical visit or absenteeism	Prevents daily activity and/or resulted in medical visit and/or absenteeism
Body Aches (Myalgia)	Noticeable but does not interfere with activity	Interferes with activity but did not necessitate medical visit or absenteeism	Prevents daily activity and/or resulted in medical visit and/or absenteeism
Headache	Noticeable but does not interfere with activity	Interferes with activity but did not necessitate medical visit or absenteeism	Prevents daily activity and/or resulted in medical visit and/or absenteeism
Chills/shivering (Feverishness)	Noticeable but does not interfere with activity	Interferes with activity but did not necessitate medical visit or absenteeism	Prevents daily activity and/or resulted in medical visit and/or absenteeism

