### **8.2 Sources of Material**

Medical history and immunization history will be obtained from the medical record and from patient report. Demographic information will be obtained from the medical record and patient report. Subjects will record solicited adverse reactogenicity events and any medical intervention sought on the day of and 7 days following vaccinations (or 7 days following mock vaccination) on the memory aid (Appendix B-E). Memory aid information will be reported to the study team during a telephone call or in the web-based REDCap system. The research staff will assess one or more of the following: weight, height, temperature, blood pressure, and pulse.

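### Does Section 7.1.2 compare systemic reactions over two diary windows in the sequential arm against one in the simultaneous arm?

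*Combined protocol and SAP*

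**What the plan says.** Section 7.1.2 is the analysis rule for Primary Objective 1. It sets the period as "Reactogenicity will be assessed for 7 days following each vaccination visit, as described in Section 5.3". It then gives proportions with exact intervals by arm, symptom and grade "for women with injection site reactogenicity within 7 days post-vaccination", taking each woman's highest grade, with a confidence interval for the difference between arms. Systemic reactions get one sentence: "Systemic reactogenicity will be presented in a similar fashion". The section does not say which diaries feed the systemic maximum, or whether that maximum is per window or across windows.

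In Table 2 of Section 5.1, vaccination at Visit 4 carries the footnote "Procedures for subjects in sequential group only". The rows for completing the memory aid and for reactogenicity carry no such restriction at Visits 4 to 6. The Visit 4 text in Section 5.1 has every woman complete the diary again, so that mock data are available "in the simultaneous group for comparison with the sequential group. Simultaneous group will only provide information for systemic reactions and oral temperature".

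Section 5.3 first defines the period as "immediately after vaccination (day 1) through post-vaccination Day 8 (day 1-8) using a standard memory aid". It later says that the procedures following the sequential arm's second vaccination are to be "performed around the same time period for the simultaneous group in a" mock fashion over Visits 4 to 6, without injection-site reactions. Section 8.2 describes women recording events "on the day of and 7 days following vaccinations (or 7 days following mock vaccination"). Appendices D and E are matching eight-day systemic forms for the two arms at Visit 4.

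**The concern.** Visit 4 is a vaccination visit for the sequential arm only. If vaccination visit is taken strictly and each woman's highest systemic grade is taken over all her vaccination windows, a sequential woman has two chances to report a symptom and a simultaneous woman has one. Fatigue, nausea, headache and body aches can occur in late pregnancy without any vaccine. A maximum over two windows is never below a maximum over one, so the sequential arm would look more reactogenic, and simultaneous vaccination better tolerated, even with no vaccine effect.

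Systemic reactions are a primary outcome (Section 2.1.1), and Section 1.1 names reactions that do not lead to a medical visit as a gap in earlier evidence. The trial is open label for staff and participants (Section 5.2.2), so an unstated rule might also be settled after the data are seen. Injection-site reactions do not raise the issue: each arm has two injection sites, each followed for one diary.

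**Working it through.** **Inputs.** From the documents: about 80 women randomised 1:1, so about 40 per arm (Sections 3.1 and 5.2.1); diary Days 1 to 8, so 8 days per window (Section 5.3); no power basis for group comparisons (Section 7). The plan gives no systemic reaction rate and no figure to reproduce. Assumed: p, the chance of reporting a given symptom in one window, equal in both arms and both windows (no vaccine effect); r, the correlation between a woman's two windows; a Newcombe interval, because the plan names no method for the difference.

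**Windows under each reading of 7.1.2**

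| Reading | Sequential | Simultaneous | Matched? |
|---|---|---|---|
| Highest grade over all diaries, mock included | 2 (16 days) | 2 (16 days) | yes |
| Each window tabulated separately | 1 v 1, twice | 1 v 1, twice | yes |
| Vaccination windows pooled, mock diary dropped | 2 (16 days) | 1 (8 days) | no |

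Only the third reading gives the imbalance.

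**Size under the third reading, any grade.** The two-window risk is q = 2p - [p² + r·p(1-p)], so the artificial excess is q - p = p(1-p)(1-r). At p = 30% and r = 0.5 this is 0.30 × 0.70 × 0.5 = 0.105, or 10.5 points. Half-widths are means over all outcomes with 40 per arm, by exact binomial enumeration.

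| p | Excess at r = 0 / 0.5 / 0.8 (points) | Mean 95% half-width at r = 0 / 0.5 / 0.8 (points) |
|---|---|---|
| 5% | 4.8 / 2.4 / 1.0 | 13.0 / 12.5 / 12.2 |
| 10% | 9 / 4.5 / 1.8 | 15.7 / 15.0 / 14.5 |
| 20% | 16 / 8 / 3.2 | 18.7 / 18.2 / 17.7 |
| 30% | 21 / 10.5 / 4.2 | 20.0 / 19.8 / 19.6 |
| 50% | 25 / 12.5 / 5 | 19.6 / 20.4 / 20.7 |

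At r = 0 the interval would exclude zero with no true effect in about 8% of trials at p = 5%, 20% at 10%, 36% at 20%, 50% at 30% and 65% at 50%. With two windows in each arm the artificial difference is 0, and the interval excludes zero in about 4 to 6% of trials.

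**Size in the cells that 7.1.2 reports.** The section tabulates by grade, and the formula applies to any-grade (or at-or-above-grade) proportions. A second window can also move a woman out of the mild cell. Suppose per-window rates of 40% mild, 15% moderate, 5% severe and 40% none, with independent windows:

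- mild: 0.80² - 0.40² = 0.48, an excess of 8 points (the formula at p = 40% would give 24);
- moderate: 0.95² - 0.80² = 0.2625, an excess of 11.25 points;
- severe: 1 - 0.95² = 0.0975, an excess of 4.75 points.

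These sum to 24 points, the any-grade excess at p = 60% (0.60 × 0.40). The single-grade cells share the any-grade excess between them.

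**Which reading the documents support.** The period sentence in 7.1.2 incorporates Section 5.3, and Section 5.3 includes the mock period. Section 5.1 gives comparison with the sequential arm as the reason for collecting mock data. Section 8.2 sets mock beside real vaccination. The words limiting events to 7 days post-vaccination are attached to injection-site reactions, where the simultaneous arm has no Visit 4 data to lose. The systemic sentence borrows the style of presentation and does not state a window.

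**The case for a change.** The strongest reply is that Section 5.3 covers collection. It does not say whether the mock window enters the simultaneous arm's proportion, is set only against the post-Tdap window, or serves as a background rate. Section 8.2 names mock vaccination expressly where it is meant and Section 7.1.2 does not. The Visit 4 forms draw the same line, since the simultaneous arm's form is headed by days since the visit and the sequential arm's by days since vaccination. At r = 0.5 and p of 20 to 30%, the excess is about half the interval half-width (8 of 18.2 points; 10.5 of 19.8), in a known direction and on a primary outcome. One sentence would remove the doubt.

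Part of this stands. Section 7.1.2 does leave the window rule unstated, and the any-grade arithmetic is right. But the listed uses of the mock window all compare or describe it; none discards it. To reach the biased result, an analyst would have to set aside data whose stated purpose is this comparison. Open-label conduct adds little, because both diaries are collected in both arms and tables by window can be produced whichever summary is chosen. The larger figures need independent windows, which is hard to credit for repeated reports of fatigue or nausea by one woman. At r = 0.8 the excess is 1 to 5 points against half-widths of about 12 to 21.

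**Conclusion.** No change to the plan is needed. Section 7.1.2 leaves out a detail that Sections 5.1, 5.3 and 8.2 supply: systemic reactions and temperature are recorded over the same two periods in both arms so that they can be compared. Analysing them over matched windows, separately or together, follows from the protocol and leaves no artificial difference.

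The size of the problem depends on a reading the protocol does not support. Under that reading the any-grade excess runs from 1 point (p = 5%, r = 0.8) to 25 points (p = 50%, r = 0), with p and r wholly assumed, and the excess in the mild cell can be well below the formula's value. Section 7 makes the trial a descriptive pilot with no test or decision threshold for reactogenicity, so even then the effect would be on a reported difference and its interval.

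Prescribing a single pooled maximum would not be a clear gain either. It would count symptoms from a period with no new vaccination as reactogenicity in the simultaneous arm, whereas tables by window remove the imbalance without doing so. The choice between those presentations can be left to the analyst.
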